### **1.3.2 Human pharmacokinetic data**

Canakinumab has the expected pharmacokinetics of an IgG1-type antibody with a low volume of distribution ( $V_{SS}=6.0$  L) and low clearance that is dependent on body weight (e.g.,  $CL=0.174$  L/day in a CAPS patient of body weight 70 kg, 0.11 L/day in a SJIA patient of body weight 33 kg and 0.23 L/day in a gout patient of body weight 93 kg). Half-lives vary between 21 and 30 days. Within the dose range studied, the pharmacokinetics of canakinumab were linear. The systemic exposure parameters, AUC and Cmax, increase in proportion to dose over the dose range of 0.30 to 10.0 mg/kg given as i.v. infusion and from 150 mg to 300 mg when administered as an s.c. injection. The absolute bioavailability of s.c. canakinumab is 70%. A mathematical model to characterize the binding kinetics of canakinumab to IL-1 $\beta$  has been created. The model successfully fits the patient data and allows estimation of canakinumab clearance and volumes of distribution, together with IL-1 $\beta$  rate of release and half-lives.

### **1.3.3 Human pharmacodynamic data**

Canakinumab binds to and inactivates IL-1 $\beta$  and blocks downstream events of IL-1 $\beta$  signaling, including IL-1 $\beta$  production, IL-1 $\beta$  pathway-related gene activation, elevation of acute phase proteins, Corporate Confidential Information and C-reactive protein (CRP), and mobilization of neutrophils and platelets from bone marrow.

Normally undetectable, serum IL-1 $\beta$  becomes detectable in humans when complexed with canakinumab. These IL-1 $\beta$ /canakinumab complexes are biologically inactive and have been utilized in all clinical studies as a surrogate PD marker because their increase reflects the reduction of free IL-1 $\beta$  levels caused by binding to canakinumab.

## **1.4 Study purpose**

This study is designed as a proof-of-concept study to assess if inhibition of IL-1 $\beta$  by canakinumab will improve lung function in association with attenuation of tissue inflammation in patients with chronic sarcoidosis, therefore allowing further development of the compound for treatment of this disease population.

## 2 Study objectives and endpoints

### 2.1 Primary objective

Primary objective	Endpoints related to primary objective

To compare the effect of ACZ885 versus placebo on the clinical disease activity of sarcoidosis patients as measured by the change from baseline in the percent predicted forced vital capacity (FVC) at week 24

	

Change from baseline in percent predicted FVC at week 24

### Rationale for Primary Outcome

FVC has been shown in sarcoidosis patients to correlate with mortality risk and is the most often used functional outcome in sarcoidosis studies, providing a benchmark for comparison against previously tested agents (Baughman et al 2012). Based on published results with corticosteroids, significant clinical responses by spirometry in sarcoidosis patients can be detected as early as 24 weeks, with maximum effect shown by 52 weeks (Baughman et al 2013).

### 2.2 Secondary objectives

Secondary objectives	Endpoints related to secondary objectives

To determine the effect of ACZ885 on decreasing the maximum standardized uptake value (SUVmax) [F-18]FDG-PET in nodules (nodular uptake regions) after 12 weeks of treatment, compared to placebo.

	

Percent change from initial scan in [F-18]FDG-PET SUVmax at week 12

To determine the effect of ACZ885 versus placebo on other parameters of pulmonary function testing (i.e., absolute FVC, FEV1, FEV1/FVC, FEV3, FEF25-75, FEV3/FVC, FEV6, TLC, RV, RV/TLC, DLco and post-bronchodilator FEV1/reversibility) in patients with sarcoidosis at 24 weeks compared to baseline

	

Lung function testing results at 24 weeks compared to baseline

To determine the effect of ACZ885 versus placebo on HRCT of patients with sarcoidosis at 24 weeks compared to initial HRCT scan as measured by side-by-side comparison by blinded reviewers and HRCT scoring

	

HRCT results at 24 weeks compared to HRCT initial scan measured by blinded reviewers and HRCT scoring

To determine the effect of ACZ885 versus placebo on the 6-minute walk test (6MWT) distance of patients with sarcoidosis at 12 and 24 weeks compared to baseline

	

6MWT results at week 12 and 24 compared to baseline

Secondary objectives	Endpoints related to secondary objectives

• To determine the effect of ACZ885 on additional [F-18]FDG-PET outcomes (i.e., SUVmean, SUVpeak and volume of the lesions) after 12 weeks of treatment compared to placebo

	

• Percent change from initial scan in additional [F-18]FDG PET outcomes at week 12

• To assess the safety and tolerability of ACZ885 in patients with sarcoidosis as measured by adverse events (AEs)

	

• Adverse events in patients taking ACZ885 compared to placebo

**Rationale for imaging with HRCT and FDG PET/CT in screening and/or secondary outcomes**

High resolution computed tomography (HRCT) is used in this study for both screening and for clinical outcome measurements. Standard plain chest radiographic views are frequently used in the diagnostic and staging processes for sarcoidosis patients. However, the chest radiographic scores (Scadding stages 0-IV) have limited value in predicting severity of pulmonary involvement and are relatively insensitive as a disease marker in therapeutic trials. HRCT (without contrast agent) provides superior resolution of lung morphology when compared to chest radiography or even conventional CT. HRCT can detect parenchymal disease in patients with normal chest radiographs or demonstrate more extensive disease in patients having only focal abnormalities on chest radiographs (Batra 1993; Drent et al 2003). Typical HRCT features of sarcoid parenchymal abnormalities include nodular densities, patchy areas of ground glass opacities, irregular linear opacities, end-stage fibrosis and honeycomb appearance. The nodules found on HRCT have been shown to likely represent confluent interstitial granulomas. Signs of distortion on HRCT are consistent with the development of fibrosis. Sequential HRCTs have shown that nodules and patchy ground glass densities are reversible, whereas honeycombing and lung distortion suggest irreversible fibrosis. Moreover, HRCT abnormalities have been reported to correlate better than radiographic stage to pulmonary functional parameters and serum biomarkers. Of particular note, relationships have been noted between HRCT findings and BAL neutrophil numbers, a marker of disease activity. HRCT correlations with other sarcoidosis disease activity markers have also been found, including BAL total cell count and serum levels of sIL-2R.

## Corporate Confidential Information

This study will use highly sensitive [F-18]FDG-PET/CT imaging to provide early evidence for effective decrease in IL-1 $\beta$ -driven inflammation on ACZ885 treatment. [F-18]FDG-PET/CT detects increased inflammation-associated metabolic activity in sarcoidosis with sensitivity of 90-100%, and decreases in [F-18]FDG-PET/CT at 24 weeks compared to baseline have been correlated with improvements in FVC over this time period (Keijzers et al 2008; Milman et al 2012; Adams et al 2014) with evidence of improvement by

serial [F-18]FDG-PET detected in sarcoid patients reported as early as 1-2 months (Brudin et al 1994; Braun et al 2008; Imperiale et al 2013). In addition, evidence suggests that low dose prednisone therapy does not appreciably alter [F-18]FDG-PET tracer uptake evaluated in a second, follow up scan while high dose (e.g., 40 mg/d) does result in PET signal reduction (Brudin et al 1994). We postulate rapid reduction in inflammasome activity upon ACZ885 treatment, and a temporally associated decrease in [F-18]FDG-PET is expected by 12 weeks. However, detectable clinical signs of improvement in pulmonary function are anticipated to require additional time after cessation of tissue inflammation by the experimental treatment. Hence, the endpoint related to pulmonary function assessment occurs later at 24 weeks. In consideration of evidence suggesting that patients with FDG PET tracer uptake in parenchymal lung tissues have active disease more likely to improve with effective intervention versus no changes in patients with negative PET findings (Keijzers et al 2011; Vorselaars et al 2015), patients in this study will undergo stratification at randomization based on baseline FDG PET/CT results. In addition, later analyses for this study will also stratify patients for the presence of lung parenchymal PET tracer uptake at baseline.

### Rationale for other secondary outcomes

Full pulmonary function tests include spirometry (FVC, FEV1, FEV1/FVC, FEF25-75, FEV3/FVC, FEV6, lung volumes (TLC, RV, RV/TLC) and gas diffusion (DLco) to allow further characterization of the patients' response to treatment. Emerging evidence suggests that sarcoidosis involves a component of small airways disease caused by constriction by peribronchiolar granulomatous inflammation (Davies et al 2000). Therefore, the following spirometry measures: FEV3, FEV3/FVC, 1-(FEV3/FVC) will be performed to assess small airway disease. (Burgel et al 2011). The Investigator needs to pay special attention to capture the FEV3 data (not always captured by traditional software; may be captured by saving the flow volume loop).

The 6MWT (including distance walked, changes in oxygenation, and Borg Questionnaire) is a practical and simple assessment of functional capacity, reflective of activities of daily living (Enright 2003) that has been increasingly applied to assess various lung diseases, including interstitial lung diseases other than sarcoidosis where it has proved useful for both predicting mortality and monitoring response to therapy. Its application in sarcoidosis studies has been more limited (Baughman et al 2007) and results should be interpreted in recognition of the multi-factorial nature of the disease (Baughman and Lower 2011).

## 2.3 Exploratory objectives

[figure not shown]
Corporate Confidential Information

Corporate Confidential Information

### 3        Investigational plan

#### 3.1      Study design

Figure 3-1      Study Design scheme

This is a 32-week, subject- and investigator-blinded, randomized, placebo-controlled, parallel-group, non-confirmatory study to assess the clinical efficacy of ACZ885 administered subcutaneously (s.c.) in 6 injections given 28 days apart (Figure 3-1). The study will randomize approximately 38 patients (targeting 30 completers) with evidence of parenchymal involvement and histologically proven, chronic pulmonary sarcoidosis of  $\geq 1$  year duration with persisting activity at baseline despite background therapy as determined by clinical history, radiologic evidence (e.g. HRCT, MRI or chest x-ray), spirometry and MMRC dyspnea scale assessments. Randomization will be stratified by positive PET parenchymal tracer uptake (yes/no). Acceptable background therapy includes a stable regimen of prednisone  $\leq 15$  mg/day and/or no more than one immune suppressive agent (i.e., methotrexate, azathioprine, leflunomide or hydroxychloroquine).

Re-screening of subjects may be allowed with the consultation of the Sponsor's medical expert.

For each subject, there will be a maximum 40-day screening period. Screening is valid for 40 days from the time of the first screening assessment. [F-18]FDG-PET/CT scans obtained locally at the study site within 8 weeks of randomization will be acceptable for baseline assessment prior to receiving the first injection of ACZ885. However, any prior [F-18]FDG-PET/CT imaging must also have been done without changes in treatment during the subsequent period leading up to study randomization.

Subjects who meet the eligibility criteria at screening will undergo evaluation of full baseline clinical and biomarker assessments prior to injection. Baseline assessments including safety laboratory evaluations and pulmonary function tests will not be available prior to dosing and for those measures eligibility criteria will be determined based on the screening results. Enrolled subjects will be randomized at a 1:1 ratio to receive treatment with either ACZ885 or placebo. On Days 1, 29, 57, 85, 113 and 141 patients will be administered s.c. dosing with ACZ885 at 300 mg or corresponding placebo treatment. All patients will return to the study center for safety and pharmacokinetic (PK) checks on an every four week basis at which time they will receive either study treatments depending on treatment arm. Additionally, patients will undergo clinical assessments that include pulmonary function tests with lung volumes, DLco, 6MWT, and clinical outcome assessments as outlined in the [Assessment Schedule](#).

At week 12, a second [F-18]FDG-PET/CT will be obtained. In addition, functional clinical measures Corporate Confidential Information will take place at this time point. The final dosing will take place on week 20, followed by a visit on week 24 Corporate Confidential Information

Corporate Confidential Information. Also included at the week 24 visit is the second HRCT assessment. Patients return for the end of study (EOS) visit at week 32.

A follow-up visit or phone call for SAEs must be performed 30 days following early discontinuation, or 8 weeks after last injection of study drug, whichever is later. If anaphylactic reactions occur after injection, two more immunogenicity samples (at the time of the event and 8 weeks later) need to be taken. Any patient who discontinues the study early will complete the Week 32, EOS visit. Patients discontinuing after week 12 will also undergo a second HRCT assessment at this visit, as assessed on a case-by-case basis by the Sponsor.

### **3.2 Rationale for study design**

A randomized, placebo-controlled, subject and investigator blinded approach is used to eliminate potential bias in reporting safety and clinical efficacy data in this first exploratory study in sarcoidosis patients.

The patient exclusion criteria of background prednisone dosing >15 mg/day is justified because chronic high dose steroids (e.g., 40 mg/day) have been reported to attenuate the [F-18]FDG-PET signal while low dose steroids do not have this effect (Brudin et al 1994).

### **3.3 Rationale for dose/regimen, route of administration and duration of treatment**

The dose of ACZ885 (canakinumab) selected for the current proof-of-concept trial is 300 mg s.c. every four weeks. This dose will ensure optimal tissue penetration for suppressing the established granulomatous inflammation over time and allow for tissue repair and recovery of organ functionality. The current label for canakinumab (Ilaris®) indicates a standard starting dosage of 2 or 4 mg/kg up to 150 mg s.c. every 8 weeks and allows for every 8 weeks dosing up to 8 mg/kg for CAPS patients  $\leq$ 40 kg and up to 600 mg s.c. for those patients  $>$ 40 kg if a satisfactory clinical response has not been achieved 7 days after treatment start. Every 4 week s.c. dosing up to 300 mg is indicated for patients with systemic juvenile idiopathic arthritis. RA patients, a relatively comparable patient population to sarcoidosis in terms of age range and inflammatory levels, have been treated with 300 mg s.c. up to 184 weeks (studies CACZ885A2201, E1 & E2) at every 2 weeks for the first 12 weeks and every 4 weeks thereafter. This dosing regimen was well-tolerated, without dose-dependent differences in AE incidence compared to every 4 weeks dosing of 150 mg s.c.

ACZ885 administered s.c. has an approximate bioavailability of 70% compared to i.v. administration. However, there are likely to be differential, organ-dependent tissue levels of ACZ885, with lung tissue penetration expected to be 10-15% of the systemic exposure (Wang et al 2008, Shah et al 2012, Shah et al 2013). Analysis of a recent failed trial of the TNF- $\alpha$  inhibitor golimumab in chronic sarcoidosis patients suggested insufficient dosing may have been a factor (Judson et al 2014). Thus, higher dosing of ACZ885 is desired for initial clinical testing of IL-1 $\beta$  blockade, a novel therapeutic target for this disease process.

The duration of every 4-week dosing to week 20 is based on the expected time of 24 weeks required for detecting functional improvement in the clinical outcome of change in percent of predicted FVC for this patient population.

In summary, in order to optimally assess the potential for ACZ885 in its first trial in sarcoidosis patients, an every 4-week dosing at 300 mg s.c. is justified to reach adequate circulating and tissue levels within the target organs for the anticipated duration required for a meaningful change in the lung inflammation and in the subsequent clinical outcomes.

### **3.4 Rationale for choice of comparator**

In this study, the placebo to ACZ885 will be used as comparator to provide objective evidence of potential AEs and other safety data as well as clinical efficacy generated from patients exposed to ACZ885.

### **3.5 Rationale for choice of background therapy**

Patients will continue on stable background therapy as established prior to study entry, thereby justifying potential treatment with placebo. Subjects will be maintained on their pre-existing stable medical regimen for treatment of preexisting medical conditions, including sarcoidosis.

### **3.6 Purpose and timing of interim analyses/design adaptations**

Corporate Confidential Information

### **3.7 Risks and benefits**

ACZ885 has not been previously administered with therapeutic intent to patients with active, chronic sarcoidosis. Therefore, no statement can be made at this time on the actual clinical benefits of ACZ885 in this patient population. However, given the mechanism of action of ACZ885 and the relevant inflammatory pathways involving IL-1 $\beta$  as discussed in the background ([Section 1.1](#)), there is a reasonable expectation that a therapeutic response can be achieved with the compound in sarcoidosis.

Overall, the development program with ACZ885 has demonstrated a good safety and tolerability profile as evidenced by a low number of study discontinuations for AEs, predominantly mild injection site reactions and no specific target organ toxicity. The AEs profile is characterized by non-specific gastrointestinal and central nervous system events, and infections predominantly of the upper respiratory tract, in some instances serious, with all infections responding to standard therapy.

The available toxicology, efficacy, safety, tolerability, lack of detectable immunogenicity and efficacy data in MWS, RA, sJIA and gouty arthritis, further support the clinical development of canakinumab in diseases in which IL-1 $\beta$  is likely to have a predominant role. However, since preventing IL-1 $\beta$  receptor signaling may alter immunologic responsiveness in unanticipated ways, patients receiving ACZ885 will be closely monitored for clinical and laboratory indicators of immune suppression and immune dysregulation, such as infection including opportunistic infections (recognizing that blocking IL-1 $\beta$  may mask fever and blunt the inflammatory response to infection), blood cells count abnormalities (including neutropenia), and development of malignancies, autoimmune manifestations and hypersensitivity reactions.

The total radiation whole body effective dose in this protocol will be less than 25 mSv; 14 mSv from HRCT scanning and 11 mSv from [F-18]FDG-PET/CT scans, including attenuation correction scans. In larger patients, a higher injected [F-18]FDG activity may be required but the total radiation exposure in these patients will not exceed 30 mSv. This amount of radiation is considered to be a moderate risk, category III (ICRP62) and is balanced against the substantial societal benefit gained from the trial. If patients have a historical [F-18]FDG-PET/CT scan that can be used as baseline scan, then only the follow up scan will be conducted as part of the clinical protocol.

As part of the spirometry assessment at Visits 101 and 107, a single dose of short-acting bronchodilators (SABA) salbutamol/albuterol will be administered. For more information please refer to product information (SmPC/USPI).

Women of child bearing potential should be informed that taking the study drug may involve unknown risks to the fetus if pregnancy were to occur during the study and agree that in order to participate in the study they must adhere to the contraception requirement for the duration of the study. If there is any question that the subject will not reliably comply, they should not be entered in the study.

There may be unknown risks of ACZ885 which may be serious and unforeseen.

### **3.7.1 Blood sample volumes**

A maximum of 350 mL of blood is planned to be collected over a period of approximately 38 weeks, from each subject as part of the study. Additional samples for monitoring of any safety findings would be in addition to this. This is not considered to be a risk for this population.

Timings of blood sample collection are outlined in the Assessment Schedule, [Section 8.2](#).

A summary blood log is provided in the Site Operations Manual, together with instructions for all sample collection, processing, storage and shipment information.

See [Section 8.9](#) regarding the potential use of residual samples.

## **4 Population**

This study will recruit patients with chronic active pulmonary sarcoidosis as defined by disease duration  $\geq 1$  year with evidence of persistent or progressive parenchymal changes as characterized by radiological evidence. A total of approximately 38 patients will be randomized to participate in the study. The sample size will be re-estimated at the interim analysis and number of randomized patients may be increased up to a maximum of 90.

The investigator must ensure that all subjects being considered for the study meet the following eligibility criteria.

Subject selection is to be established by checking through all inclusion/exclusion criteria at screening and first baseline prior to the first injection. Safety laboratory evaluations and pulmonary function tests taken at first baseline will not be available prior to first injection, and screening values should be used for inclusion in the study. A relevant record (e.g., checklist) of the eligibility criteria must be stored with the source documentation at the study site.

Deviation from any entry criterion excludes a subject from enrollment into the study.

#### **4.1 Inclusion criteria**

Pulmonary sarcoidosis patients eligible for inclusion in this study must fulfill **all** of the following criteria:

1. Written informed consent must be obtained before any assessment is performed.
2. Male and female subjects ages 18 to 80 years of age (both inclusive)
3. Subjects must weigh at least 50 kg to participate in the study
4. Able to communicate well with the investigator and to understand and comply with the requirements of the study.
5. Disease duration of  $\geq 1$  year
6. Clinically active disease demonstrated either by a biopsy (any organ) or by bronchoalveolar lavage (lymphocytosis  $>15\%$ ,  $CD4^+/CD8^+$  ratio  $>3.5$ ,  $CD103^+CD4^+/CD4^+$  ratio  $<0.2$ ) ([Heron et al 2008](#)). Patients must also have all of the following criteria:
  - MMRC dyspnea scale  $\geq 1$
  - Threshold FVC 50 - 90% of predicted ([Pellegrino et al 2005](#), [Vorselaars et al 2015](#))
  - Evidence of parenchymal lung involvement by HRCT at screening or by historical radiological evidence (e.g. CT, MRI or x-ray)

#### **4.2 Exclusion criteria**

Pulmonary sarcoidosis patients fulfilling any of the following criteria are not eligible for inclusion in this study:

1. History of known hypersensitivity to canakinumab
2. Current inhaled use of tobacco products (urine cotinine level  $> 500$  nanograms/mL) at screening
3. Use of other investigational drugs at the time of enrollment, or within 5 half-lives of enrollment, or until the expected PD effect has returned to baseline, whichever is longer, or longer if required by local regulations
4. Previous exposure to concomitant treatment according to the following criteria:
  - a. Prednisone  $>15$  mg/day or changes in prednisone dose in the 8 weeks prior to screening
  - b. More than one immune-modulator (i.e., methotrexate, azathioprine, leflunomide, hydroxychloroquine) or changes in their dosing levels within 12 weeks of randomization. Refer to [Section 5.2](#), 'Prohibited treatments' for additional details
  - c. Mycophenolate use within 12 weeks of randomization

5. Prior treatment with any biologic drug targeting the immune system within 180 days of randomization or history of any previous use of rituximab
6. Diagnosis of pulmonary hypertension requiring treatment
7. History of bleeding disorder
8. Extra-pulmonary sarcoidosis as primary treatment indication (e.g., involving brain, heart, eye and renal disease with significant hypercalcemia)
9. Any conditions or significant medical problems which in the opinion of the investigator immune-compromise the patient and/or places the patient at unacceptable risk for immunomodulatory therapy, such as:
  - Absolute neutrophil count (ANC) <LLN (1,500/ $\mu$ l)
  - Thrombocytopenia CTCAE v4.03 Grade 1: Platelets <LLN ( $75.0 \times 10^9/L$ )
  - Any active or recurrent bacterial, fungal (with exception of onychomycosis) or viral infection
  - Presence of human immunodeficiency virus (HIV) infection, active hepatitis B or hepatitis C infections based on screening lab results
  - Presence of active or latent tuberculosis (TB). If historical Tb result is available, Tb status needs to be confirmed pre-randomization as determined by screening laboratory measurements.
  - Clinical evidence or history of multiple sclerosis or other demyelinating diseases, or Felty's syndrome
10. Live vaccinations within 3 months prior to screening
11. Current severe progressive or uncontrolled disease, which in the judgment of the clinical investigator renders the patient unsuitable for the trial
12. Inability or unwillingness to undergo repeated venipuncture (e.g., because of poor tolerability or lack of access to veins)
13. Donation or loss of blood (amount depending on age and weight, 10-20% or more of volume, within 8 weeks prior to first dosing, or longer if required by local regulation)
14. History of malignancy of any organ system (other than localized basal cell carcinoma of the skin), treated or untreated, within the past 5 years, regardless of whether there is evidence of local recurrence or metastases
15. Contraindications to FDG-PET scan investigations, such as severe claustrophobia or uncontrolled diabetes
16. Pregnant or nursing (lactating) women, where pregnancy is defined as the state of a female after conception and until the termination of gestation, confirmed by a positive hCG laboratory test

17. Women of child-bearing potential, defined as all women physiologically capable of becoming pregnant, unless they are using basic methods of contraception during dosing of investigational drug. ***Basic contraception methods include:***

- Total abstinence from heterosexual intercourse (when this is in line with the preferred and usual lifestyle of the subject). Periodic abstinence (e.g., calendar, ovulation, symptothermal, post-ovulation methods) and withdrawal are not acceptable methods of contraception
- Female sterilization (have had surgical bilateral oophorectomy with or without hysterectomy), total hysterectomy or tubal ligation at least 6 weeks before taking investigational drug. In case of oophorectomy alone, only when the reproductive status of the woman has been confirmed by follow up hormone level assessment
- Male sterilization (at least 6 months prior to screening). For female subjects on the study, the vasectomized male partner should be the sole partner for that subject.
- Barrier methods of contraception: condom or occlusive cap (diaphragm or cervical/vault caps). For UK: with spermicidal foam/gel/film/cream/vaginal suppository
- Use of oral, injected or implanted hormonal methods of contraception or other forms of hormonal contraception that have comparable efficacy (failure rate <1%), for example hormone vaginal ring or transdermal hormone contraception or placement of an intrauterine device (IUD) or intrauterine system (IUS)

In case of use of oral contraception women should be stable on the same pill for a minimum of 3 months before taking study drug

Women are considered post-menopausal and not of child bearing potential if they have had 12 months of natural (spontaneous) amenorrhea with an appropriate clinical profile (e.g., age appropriate, history of vasomotor symptoms) or have had surgical bilateral oophorectomy (with or without hysterectomy), total hysterectomy or tubal ligation at least six weeks ago. In the case of oophorectomy alone, only when the reproductive status of the woman has been confirmed by follow up hormone level assessment is she considered not of child bearing potential.

18. History of drug or alcohol abuse within the 12 months prior to dosing, or evidence of such abuse as indicated by the laboratory assays

No additional exclusions may be applied by the investigator, in order to ensure that the study population will be representative of all eligible patients.

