## 5      Restrictions for Study Subjects

During recruitment, screening/informed consent review, and baseline visit, the subjects must be informed and reminded of the following restrictions:

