### 5.1    Contraception requirements

Please refer to exclusion criteria ([Section 4.2](#)) for details of contraception requirements for the study.

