### 5.2    Prohibited treatment

Use of the treatments displayed in the table below are NOT allowed during the screening period or after the start of study treatment due the concern for increased potential immunosuppressant-related conditions. These are prohibited for the duration of the study until 30 days after the last study visit.

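### Exclusion 17 ends required contraception with dosing, about 8 to 12 weeks before the whole-study period in Protocol Section 3.7, and Section 5.1 sends sites only to the shorter clause

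*Protocol*

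**What the plan says.** The contraception period appears in two places, with two lengths.

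- **Protocol 4.2, exclusion 17.** Women of child-bearing potential are excluded "unless they are using basic methods of contraception during dosing of investigational drug". No period after the last dose is given.
- **Protocol 3.7, Risks and benefits.** Such women must agree that, to take part, "they must adhere to the contraception requirement for the duration of the study". The section adds: "If there is any question that the subject will not reliably comply, they should not be entered in the study".

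Two further places bear on which text a site will use.

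- **Protocol 5 and 5.1.** Section 5 introduces the points on which "the subjects must be informed and reminded of the following restrictions". Section 5.1, the contraception item, names no duration. It sends the reader to the exclusion criteria "for details of contraception requirements for the study".
- **Protocol 5.2.** The next restriction, on prohibited treatments, has an explicit end: "These are prohibited for the duration of the study until 30 days after the last study visit".

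On timing, Section 3.1 opens with "This is a 32-week, subject- and investigator-blinded, randomized". It schedules six injections, the last on Day 141 (week 20), and an EOS visit at week 32. The assessment schedule puts the EOS visit on Day 224. Section 3.3 also ends dosing at week 20, whereas the synopsis describes four-weekly administration over 24 weeks in all.

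**The concern.** Exclusion 17 is the operative criterion: it is what a site checks at entry, and it is the only place Section 5.1 cites. Its period is shorter than the one in the risk-benefit narrative, which Section 5.1 does not cite. Section 3.7 also speaks only of the contraception requirement without naming a section, so a reader could trace it back to exclusion 17 and its shorter period.

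A site that takes the duration from exclusion 17 alone would tell a woman she may stop contraception once dosing ends. At that point a long-half-life antibody is still circulating. The scheduled pregnancy tests are at screening, Day 1 and EOS only, so a pregnancy beginning after the last dose might not be picked up by protocol testing until Day 224.

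What is at stake is participant safety and a consistent instruction across sites. The efficacy analysis is not involved.

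**Working it through.** **Inputs**
- Dosing days 1, 29, 57, 85, 113 and 141 (Protocol 3.1).
- Week 24 visit on Day 169 and EOS visit on Day 224, each with a window of plus or minus 5 days (Protocol 8.1).
- Half-life 21 to 30 days (Protocol 1.3.2).

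**Step 1: reproduce the plan's timeline.** Six doses 28 days apart from Day 1 give a last dose on 1 + 5 × 28 = Day 141, and (141 − 1)/7 = week 20, as stated. EOS is 224/7 = week 32, as stated.

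**Step 2: when does dosing end?** The documents allow two readings.
- At the last injection, Day 141 (Sections 3.1 and 3.3).
- At the end of the last four-week interval, 141 + 28 = Day 169 (the 24 weeks in the synopsis).

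**Step 3: shortfall against Section 3.7, taking the study to end at EOS**

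| End of dosing | Gap to Day 224 | Weeks | Range if visit windows shift the gap by up to 10 days |
|---|---|---|---|
| Day 141 | 224 − 141 = 83 days | 11.9 | 73 to 93 days (10.4 to 13.3 weeks) |
| Day 169 | 224 − 169 = 55 days | 7.9 | 45 to 65 days (6.4 to 9.3 weeks) |

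Both readings fall short of Section 3.7, by about 8 to 12 weeks at the planned dates.

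**Step 4: drug remaining in that period.** Fraction of the last-dose level = 2^(−t / half-life), where t is days since the last dose. This assumes simple exponential decline and ignores absorption.

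| Day | t | Half-life 21 days | Half-life 30 days |
|---|---|---|---|
| 169 | 28 | 2^(−28/21) = 39.7% | 2^(−28/30) = 52.4% |
| 224 | 83 | 2^(−83/21) = 6.5% | 2^(−83/30) = 14.7% |

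The uncovered weeks are therefore weeks of continuing exposure. The documents give no concentration below which fetal exposure would be considered unimportant, so these figures describe exposure, not risk.

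**Step 5: effect of aligning exclusion 17 with Section 3.7.** Cover then runs to Day 224. That adds 83 days counted from the last injection, or 55 days counted from the end of the last interval, and the shortfall for completers is zero.

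**The case against.** The strongest reply is that Section 3.7 makes whole-study adherence a condition of participation. The two texts can be followed together by applying the longer one, and a site that reads the whole protocol covers women to Day 224. Pregnancy tests and pregnancy reporting are also in place, the trial plans only about 38 patients, and the number of women of child-bearing potential is unknown. All of this stands, and it keeps the consequence modest. It does not remove the mismatch, because Section 5.1 leads sites away from the text that holds the longer period.

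A reader might also infer more than the documents support:

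- **That the protocol lacks a requirement after dosing.** It does not; Section 3.7 supplies one.
- **That women are actually told the shorter period.** The consent pages were removed before review and the Site Operations Manual is not available, so this cannot be known.
- **That Section 3.7 collides with the closing rule of Section 4.2, "No additional exclusions may be applied by the investigator".** The conflict is thin. The instruction not to enter unreliable compliers is the protocol's own text, not an investigator's addition, and inclusion 4 already requires the ability to comply with study requirements.
- **That the residual drug levels show fetal harm, or fix a safe interval.** Section 1.2, which holds the reproductive toxicity text, is redacted.
- **That a set interval after the last dose, such as 12 weeks, is needed to correct the inconsistency.** Neither text contains one. The case for it rests on women who discontinue early and have an EOS visit soon after their last dose, but the protocol gives no early date for that visit; it calls it the Week 32 visit throughout.

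**Conclusion.** The point holds as an internal inconsistency in the contraception duration. For a woman who completes the study, exclusion 17 read alone ends cover 55 days (from Day 169) or 83 days (from Day 141) before the period Section 3.7 sets.

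This wording mismatch is certain, since both clauses and the cross-reference are in plain text. The size in weeks rests on the planned visit days and on taking the study to end at the EOS visit. The statement that drug remains rests on the stated half-lives and first-order decline. The harm itself cannot be quantified from these documents, and it arises only where a site relies on exclusion 17 without Section 3.7.

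It is worth correcting because a written eligibility rule is shorter than the protocol's own requirement on a safety matter, and aligning them costs almost nothing.

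**What to change.** In exclusion 17, replace the limit to the dosing period with: *for the duration of the study (through the end-of-study visit)*. State the same duration in Section 5.1 in place of the bare cross-reference. Section 3.7 can stay as it is. Using its wording also avoids narrowing it at the front end, where the study may include up to 40 days of screening before the first dose.

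The cost is a few words in one criterion and one line in Section 5.1, in the next written amendment, with a check that the consent form and site materials give the same period. No visit, test, sample size or analysis changes.

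Separately, and not as part of this correction, the sponsor may wish to decide from its own reproductive toxicity and pharmacokinetic data whether women who discontinue early need a minimum period after their last dose.
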